**ACQ control categories**

- ACQ total scores at each visit will be summarized by the following asthma control categories:
- a) well controlled, i.e., ACQ total score  $\leq 0.75$ ,
  - b) partially controlled i.e.,  $0.75 < \text{ACQ total score} < 1.5$ ,
  - c) inadequately controlled, i.e., ACQ total score  $\geq 1.5$ .
- Shift from baseline at each visit in ACQ total score will also be summarized by the following categories:
- a) Improved (defined as from inadequately controlled at baseline to partially or well controlled at visit, or from partially controlled at baseline to well controlled at visit)
  - b) Unchanged (defined as same asthma control category at visit and baseline)
  - c) Worsening (defined as from well controlled at baseline to partially or inadequately controlled at visit, or from partially controlled at baseline to inadequately controlled at visit)

**Responder Status according to ACQ Total Score**

- A participant will be considered a responder according to ACQ total score if their ACQ total score has decreased at least 0.5 units from the baseline ACQ total score.
- A participant will be considered a non-responder if their ACQ total score has decreased by less than 0.5 units, has not changed, or has increased compared to baseline.
- Missing data will be handled as detailed in Section [11.7.2](#).

**St. George’s Respiratory Questionnaire (SGRQ)**

**General**

- Details for how to score the SGRQ, including handling of missing data, are outlined in the

St. George's Respiratory Questionnaire (SGRQ)

SGRQ manual (June, 2009).
 
 
• Changes from baseline in domain and total score will be calculated.
 
• If the language of the SGRQ conducted at a post-treatment visit is different to the language used at Day 1 baseline, all SGRQ scores at that visit and all subsequent visits will be set to missing.
 
• If the language of the SGRQ is missing at any visit (including Baseline) and is the same at all remaining non-missing visits, the language at the missing visit will be assumed to be unchanged
 

Responder Status according to SGRQ Total Score

 
• A participant will be considered a responder according to SGRQ total score if their SGRQ total score has decreased at least 4 units from the baseline SGRQ total score.
 
• A participant will be considered a non-responder if their SGRQ total score has decreased by less than 4 units, has not changed, or has increased compared to baseline.
 
• Missing data will be handled as detailed in Section 11.7.2.
 

Asthma Quality of Life Questionnaire (AQLQ)
General

 
• Details for how to score the AQLQ, including handling of missing data, are outlined in the AQLQ manual (May, 2012).
 
• Changes from baseline in total score will be calculated.
 
• If the language of the AQLQ conducted at a post-treatment visit is different to the language used at Day 1 baseline, all AQLQ scores at that visit and all subsequent visits will be set to missing.
 
• If the language of the AQLQ is missing at any visit (including Baseline) and is the same at all remaining non-missing visits, the language at the missing visit will be assumed to be unchanged
 

Responder Status according to AQLQ Total Score

 
• A participant will be considered a responder according to AQLQ total score if their AQLQ total score has increased at least 0.5 from the baseline AQLQ total score.
 
• A participant will be considered a non-responder if their AQLQ total score has increased by less than 0.5 units, has not changed, or has decreased compared to baseline.
 
• Missing data will be handled as detailed in Section 11.7.2.
 

Calculation of Daily eDiary Endpoints
General

 
Efficacy endpoints based on diary assessments include E-RS total score and subscale scores (breathlessness, cough & sputum, chest symptoms), Home Daily AM (trough) and PM FEV1, AM and PM PEF, percentage of symptom-free days, percentage of rescue medication-free days, and daily rescue medication use.
 
The detailed derivations for diary data are provide in Section 5.2 for baseline value and Section 5.3.2 for post-baseline values.
 
If the language of the E-RS conducted post-randomization is different to the language used during the baseline period, all E-RS scores post-randomization will be set to missing.
 
The E-RS scoring instructions can be found in Appendix B of the User Manual [E-RS (Evaluating Respiratory Symptoms (E-RS™) in COPD (E-RS™: COPD) User Manual, Version 5.0. March, 2016].
 

Symptom-free days											

 
For a given day, a participant has a symptom-free day if the responses to both the evening (measures symptoms during the day) and following morning's (measures nocturnal symptoms from the previous night) assessments indicate no symptoms.
 
A participant has a symptom-free day if the participant has no asthma symptoms AND the participant's activities are not at all limited AND the participant has no nocturnal awakenings due to asthma symptoms, per diary data as in the table below:
 
											

  
 Assessment Time	Question	Outcome	
   
 Morning	Did you wake up due to asthma symptoms (i.e. wheezing, coughing, shortness of breath, or chest tightness)?	No	
 
 Evening	Please describe the severity of your asthma symptoms today (i.e. cough, wheeze, chest tightness, shortness of breath)	No asthma symptoms	
 
 How limited were you in your activities today because of your asthma	Not at all limited	
  
	Assessment Time	Question	Outcome	Morning	Did you wake up due to asthma symptoms (i.e. wheezing, coughing, shortness of breath, or chest tightness)?	No	Evening	Please describe the severity of your asthma symptoms today (i.e. cough, wheeze, chest tightness, shortness of breath)	No asthma symptoms	How limited were you in your activities today because of your asthma	Not at all limited
Assessment Time	Question	Outcome									
Morning	Did you wake up due to asthma symptoms (i.e. wheezing, coughing, shortness of breath, or chest tightness)?	No									
Evening	Please describe the severity of your asthma symptoms today (i.e. cough, wheeze, chest tightness, shortness of breath)	No asthma symptoms									
	How limited were you in your activities today because of your asthma	Not at all limited									

 
If any of these outcomes is missing the symptom free day status will be set to missing
 
If there is more than one morning or evening assessment assigned to a study day, then all records need to concur that no symptoms occurred for it to be considered a symptom free day
 
Percentage of symptom free days will be calculated as the (number of symptom free days/total
 
											

number of days with non-missing symptom free day status)*100 within a given reporting period.
 
 
• If >50% of days within a reporting period have missing symptom free day status, the percentage of symptom free days will be considered missing for that period.
 


Rescue Medication free days
 
 
• For a given day, a participant has a rescue medication-free day if the responses to both the evening (measures rescue medication use during the day) and following morning's (measures rescue medication use during the previous night) assessments indicate no use of rescue medication.
 
• If either the evening and following morning's assessment is missing then the days rescue medication use is set to missing.
 
• If there is more than one morning or evening assessment assigned to a study day, then all records need to concur that no rescue medication was taken for it to be considered a rescue medication free day
 
• Percentage of rescue medication free days will be calculated as the (number of rescue medication free days/total number of days with non-missing rescue medication free day status)*100 within a given reporting period.
 
• If >50% of days within a reporting period have missing rescue medication free day status, the percentage of rescue medication free days will be considered missing for that period.
 

Number of puffs per day
 
 
• For a given day, the number of puffs will be the sum of the evening number of puffs (measures rescue medication use during the day) and following morning's number of puffs (measures rescue medication use during the previous night).
 
• If a participant only has one of these assessments, then the number of puffs will be set to missing.
 
• If a participant has both an evening and a morning assessment and > 1 assessment at either of those timepoint, use the maximum value reported for the timepoint (i.e. number of puffs=max(morning) + max(evening))
 

Healthcare Resource Utilization
 
 
• The total number of unscheduled asthma related healthcare resource utilization, including telephone contacts, specialist nurse visits, visits to a physician's office, home visits (day and night time), outpatient visits, visits to urgent care, visits to the emergency department, and hospitalizations associated with the participant's worsening of symptoms will be calculated.
 
		

The following data will be included in the summaries
		
Analysis	Time point	Data to be included (i.e. from participants first dose up to date/study day specified)
On- and post-treatment	1-24	
 
- If participants planned EOS visit is week 24: EOS/EW visit/study conclusion date*/date of death
 
- If participants planned EOS visit is later than week 24 use data up to the minimum of study day 169, EW study conclusion date*, date of death.
 

	1-52	
 
- All health utilization data for participants with planned
 

	with $\geq 36$ planned exposure	EOS visit at Week 36 or Week 52.
*if no study conclusion date then use last contact date		

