## 11.4. Appendix 4: Study Phases

Study phases for assessments scheduled at a set time will be defined in accordance with the planned relative time of the assessment.

Any events/assessments for participants not in the ITT population will be assigned a Pre-treatment phase.

For all events and assessments, the study phases will be defined as follows:

Study Phase	Definition
Screening/Run-In period	Visit 1 date $\leq$ Event Onset Date or Assessment Date/Time $<$ Visit 2 date or date of first dose of Stabilization treatment, whichever is later
Stabilization period	Date of first dose of Stabilization treatment $\leq$ Event Onset Date or Assessment Date/Time $<$ Randomized treatment start date. Note: if baseline assessment and done on treatment start date then assumed to be done prior to treatment start.
On-Treatment	Randomized treatment start date $\leq$ Event Onset Date or Assessment Date/Time $\leq$ Study Treatment Stop Date +1 or any assessment with a missing or partial date unless there is evidence it was not on-treatment
Post-Treatment 	Randomized Treatment Stop Date +1 $<$ Event Onset Date or Assessment Date/Time $\leq$ Last Scheduled Clinic Visit (i.e., Visit 8 [EOS Visit] or Early Withdrawal Visit [EW])  Note: if any participant does not receive a dose of randomized treatment then all post-baseline data prior to EW or EOS visit is considered as post-treatment.
Post-Study	Event Onset Date $>$ Last Scheduled Clinic Visit (i.e., Visit 8 (EOS Visit) or Early Withdrawal Visit)  +1 day Note, for participants who continue in the study after IP discontinuation (i.e. where treatment discontinuation date $<$ Visit 8 (EOS visit) date or EW visit date), the rule will be: Event Onset Date $>$ Last Scheduled Clinic Visit (i.e. Visit 8 (EOS Visit) or EW Visit) 
 : Applicable only for participants who continue in the study after IP discontinuation.  If a subject is lost to follow up and does not have an EoS or EW visit, their study conclusion date will be used if available. If no study conclusion date is available, the last contact date will be used.	

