### 11.5.2. Reporting Standards

Reporting Standards	
General	

 
Displays will use the term “Subjects” to refer to “Participants”.
 
The current GSK Pooled Data Standards Library (IDSL) will be applied for reporting, unless otherwise stated: 
 
4.03 to 4.23: General Principles
 
5.01 to 5.08: Principles Related to Data Listings
 
6.01 to 6.11: Principles Related to Summary Tables
 
7.01 to 7.13: Principles Related to Graphics
 
 
 
	
Formats	

 
All data (including data collected following study treatment discontinuation [post-treatment]) will be reported according to the treatment to which the participant was randomized unless otherwise stated. However, there may be additional adhoc displays for individual participants using the actual treatment received.
 
The reported precision of data will follow IDSL statistical principles but may be adjusted to a clinically interpretable number of decimal places.
 
In most cases, percentages between 1% and 99%, inclusive, will be rounded to integers. Percentages greater than 0%, but less than 1%, will be reported as <1%, and percentages greater than 99%, but less than 100%, will be reported as >99%. For some rare events, percentages may be reported in 1 decimal point. In this case, percentages greater than 0%,
 
	

Reporting Standards	

but less than 0.1%, will be reported as <0.1%.
 
 
Numeric data will be reported at the precision collected on the eCRF.
 
The reported precision from non eCRF sources will follow the IDSL statistical principles but may be adjusted to a clinically interpretable number of decimal places.
 
	
Planned and Actual Time	

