**Asthma Control Questionnaire (ACQ)**

- average of all non-missing item responses [Asthma Control Questionnaire, Background, Administration and Analysis, May, 2012].
- Only one of the first five item responses are allowed to be missing in calculating the total scores for all versions of ACQ.
  - If the language of the ACQ conducted at a post-baseline visit is different to the language used at Day 1 baseline, all ACQ scores at that visit and all subsequent visits will be set to missing.
  - If the language of the ACQ changes during the run-in phase, stabilization phase and randomization, the change in these periods will only be calculated where the language remained consistent.
  - If the language of the ACQ is missing at any visit (including Baseline) and is the same at all remaining non-missing visits, the language at the missing visit will be assumed to be unchanged

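### As worded, the SGRQ and AQLQ language-change rules reach only post-treatment visits, so changed-language scores on treatment would be kept

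*SAP*

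**What the plan says.** SAP 11.6.3 (Appendix 6, Efficacy) has a language rule for each patient-reported instrument.

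- **SGRQ:** "If the language of the SGRQ conducted at a post-treatment visit is different to the language used at Day 1 baseline", then "all SGRQ scores at that visit and all subsequent visits will be set to missing".
- **AQLQ:** "If the language of the AQLQ conducted at a post-treatment visit is different to the language used at Day 1 baseline", with the same consequence for AQLQ scores.
- **ACQ:** "If the language of the ACQ conducted at a post-baseline visit is different to the language used at Day 1 baseline", again with scores at that visit and later ones removed.
- **E-RS:** "If the language of the E-RS conducted post-randomization is different to the language used during the baseline period", in which case every E-RS score after randomization is removed.

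Post-treatment is a defined term in this SAP. Appendix 4 (Section 11.4) starts the phase after "Randomized Treatment Stop Date +1" and footnotes it "Applicable only for participants who continue in the study after IP discontinuation". A note in the same row adds participants who never took randomized treatment, whose post-baseline data before the final visit are all classed as post-treatment. Section 11.5.2 uses the term the same way: "All data (including data collected following study treatment discontinuation [post-treatment]) will be reported according to the treatment to which the participant was randomized". Section 6.1 plans a summary of participants as on-treatment or post-treatment at each clinic visit.

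**The concern.** A language rule is there to remove change scores whose two ends were collected in different languages. Whether the participant is still taking study drug has no bearing on that. With this trigger, treatment status decides whether the score is removed.

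Three things follow if the text is programmed literally:

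- Scores that the rule appears designed to remove stay in the analysis when they are collected on treatment.
- Instruments are handled differently at one visit. A participant who switches language on treatment loses ACQ-7 and keeps SGRQ.
- In the SGRQ and AQLQ responder analyses a missing score counts as non-response (SAP 11.7.2). A changed-language score off treatment becomes a non-response, while one on treatment is scored as observed.

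SGRQ total score at Week 24 is tested at Level 3 (UMEC 62.5 mcg) and Level 7 (UMEC 31.25 mcg) of the hierarchy in SAP 5.6, so its derivation should have a single reading.

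**Working it through.** No arithmetic applies: the point turns on the scope of a term. The steps are as follows.

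**1. Which visits does the trigger cover?** Under Appendix 4, an assessment from treatment start up to the stop date plus one day is on-treatment; a later one, up to the last scheduled clinic visit, is post-treatment. Protocol 6.1 has completers take their last dose at Visit 8/EOS, so their SGRQ and AQLQ visits are all on-treatment. Read literally, the trigger never applies to a completer.

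**2. Does any other rule fill the gap?** The remaining language bullet for SGRQ and AQLQ says what to assume when the language is missing at a visit. Nothing else in the SAP deals with an on-treatment language change for these two instruments.

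**3. What happens to particular participants?** The SGRQ model uses Weeks 12 and 24 (SAP 7.3.5.1). Suppose the language differs from Day 1 at both visits:

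| Participant | SGRQ as worded | Same case under the ACQ wording |
|---|---|---|
| On treatment at both visits | Week 12 kept, Week 24 kept | both missing |
| Stopped drug before Week 12, stayed in study | both missing | both missing |
| On treatment at Week 12, off drug but in study at Week 24 | Week 12 kept, Week 24 missing | both missing |
| Never dosed, attends visits | both missing | both missing |

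The two wordings differ only in the on-treatment cells. Off treatment they delete the same scores.

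**4. How does this sit with the planned analysis?** SAP 7.3.5.1 analyses SGRQ by MMRM under a treatment-policy strategy, and Section 7 says that on- and post-treatment data are both used. Nothing there calls for a language rule that depends on treatment status.

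**5. How many participants are affected?** The documents do not report language changes, or how many of the people concerned had stopped treatment. The number cannot be derived.

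**The case against.** The strongest reply is that this is a slip of the pen and not a chosen method. The SGRQ and AQLQ bullets match the ACQ bullet apart from this term and the instrument name, and they set the visit against the Day 1 baseline. The neighbouring bullet fills in a missing language by looking across all visits, which would have little purpose if language mattered only off drug. The programmed derivation may already treat the rule as post-baseline. That reading of intent is probably right, and it stands. It does not change what the text says: someone coding or checking from the Appendix 4 definitions would reach a different dataset.

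Several stronger inferences are tempting, and the documents do not support them:

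- **That the rule costs the treatment-policy estimand its off-drug data.** The post-baseline wording deletes the same off-drug scores, as the table shows, so correcting the rule restores none of them. The fault is unequal handling and the retention of on-treatment scores.
- **That only discontinuers lose scores.** Participants never dosed are also classed as post-treatment.
- **That a count of affected participants can be given.** Any figure would rest on an assumed switching rate with no source in the documents. Applying such a rate to all 2439 randomized (766 + 643 + 399 + 631, SAP 5.4) would also be too broad. Each SGRQ test contrasts four of six equally allocated arms, about 1626 people (4/6 × 2439). Changes after Week 24 do not enter the model, and changes in people already off treatment are handled the same way under either wording.
- **That a hierarchy result is at risk.** Allocation is randomized and double-blind, and nothing in the documents suggests that language changes differ by arm.

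**Conclusion.** The rule is wrong as written for SGRQ and AQLQ. Taken with the SAP's own definition of post-treatment, it would keep changed-language scores on treatment and remove them off treatment, unlike the ACQ and E-RS rules. It is best described as a probable drafting slip in an operative derivation rule, and it is minor. The number of participants affected is unknown. That the effect is small is a judgement: it assumes that few participants change questionnaire language during the study. The confirmatory relevance is confined to SGRQ at Levels 3 and 7. AQLQ is outside the hierarchy, and there is no evidence that any test result would differ.

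**What to change.** In the SGRQ and AQLQ bullets of SAP 11.6.3, replace *post-treatment visit* with *post-baseline visit*, so that both match the ACQ rule. Before unblinding, check that the programmed derivation for both instruments applies the corrected trigger. The SAP synopsis already commits to settling decisions about the final analysis by source data lock on treatment-blinded data, so the correction fits that step.

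The cost is one changed term in each of two bullets and a short programming check. No new data or additional analysis is needed. A blinded count of language changes by visit, taken during that check, would show whether the point has any practical effect.

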Level 9: Secondary endpoint, UMEC 62.5 mcg: Mean change from baseline in E-RS score over Weeks 21-24 (inclusive) of the treatment period.

One comparison based on pooled data:

(FF/UMEC/VI 100/62.5/25, 200/62.5/25) vs. (FF/VI 100/25, 200/25)

Test needs to be significant at 0.05 level in order to move to Level 10 test.

Level 10: Secondary endpoint, UMEC 31.25 mcg: Mean change from baseline in E-RS score over Weeks 21-24 (inclusive) of the treatment period.

One comparison based on pooled data:

(FF/UMEC/VI 100/31.25/25, 200/31.25/25) vs. (FF/VI 100/25, 200/25)

For any endpoints and/or treatment comparisons not mentioned in the multiplicity adjustment plan, treatment comparisons will be made without adjusting for multiplicity.

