### Model Specification

- Analyses are based on the treatment policy (de facto) type estimand using the pooled FF doses.
- Baseline definitions are provided in Section 5.2.
- The change from baseline for each endpoint will be analyzed using a Mixed Models Repeated Measures (MMRM) model.
- Terms in the MMRM model
  - Period:
    - SGRQ: Clinic visits Week 12 and 24
    - ACQ-7: Clinic visits at Week 4, 12 and 24
    - E-RS: Weeks 1-4, Weeks 5-8, Weeks 9-12, Weeks 13-16, Weeks 17-20, Weeks 21-24.
  - Covariates:
    - Categorical: treatment group, sex, region, pre-study ICS dosage at screening and period.
    - Continuous: age, baseline value
  - Interaction: baseline\*period, treatment\*period
    - Repeated: period
  - All 6-arm data are included in the model.
  - LSMESTIMATE statement will be used with the treatment code as specified Section 7.
  - For the E-RS endpoint, the average treatment effect over the 24-week treatment period will also be obtained from the model and presented in the analysis output.
- The model will be fitted with an unstructured variance-covariance matrix.
- The OM option in SAS will be used to derive the LS means based on the distribution of the covariates observed in the data

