### 11.7.2. Handling of Missing Data

Element	Reporting Detail
General	
 
• Missing data occurs when any requested data is not provided, leading to blank fields on the collection instrument:               
 
○ These data will be indicated by the use of a "blank" in participant listing displays unless all data for a specific visit are missing in which case the visit is not displayed in the listing.
 
○ Answers such as "Not applicable" and "Not evaluable" are not considered to be missing data and should be displayed as such.
 
○ No imputation will be made for any missing numerical data, except in the sensitivity analysis of primary endpoints to assess the impact of missing data on study results. Missing data will generally not be considered in the calculation of percentages (i.e., the denominator will not include participants who have missing data at a given time point).
 
 
 

Responder Analysis	
 
• Participants with a missing baseline will have responder status as missing.
 
• Participants with missing data at scheduled clinic visit, regardless of treatment status, will be considered as non-responders.
 
• For ACQ/SGRQ/AQLQ, participants that have withdrawn from study prior to the visit Week 24 will be imputed as non-responders at all visits after early
 

Element	Reporting Detail
	
withdrawal visit where the assessment was expected to be performed, up to Week 24.
 
 
For E-RS and subscales, participants that have withdrawn from study prior Week 24 in question will be imputed as non-responders at time periods post-study withdrawal. This includes time periods up to and including Weeks 21-24.
 

Asthma Control Based on ACQ	
 
Participants with missing data at Week 12 or Week 24 will be classified as not achieving asthma control regardless of reasons in the summaries and analyses.
 
Participants with missing data at baseline will be excluded from the analysis, due to the inclusion of baseline as a covariate.
 

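### Read literally, the E-RS language rule deletes every post-randomization score after any language mismatch, including scores recorded in the baseline language before a switch

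*SAP*

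**What the plan says.** The rule is in SAP Section 11.6.3, under the calculation of daily eDiary endpoints. Its trigger reads "If the language of the E-RS conducted post-randomization is different to the language used during the baseline period", and its consequence is that "all E-RS scores post-randomization will be set to missing". No date, visit or period limits the deletion.

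The parallel rules in the same section do carry a limit:

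- ACQ: "all ACQ scores at that visit and all subsequent visits will be set to missing"
- SGRQ: "all SGRQ scores at that visit and all subsequent visits will be set to missing"
- AQLQ: "all AQLQ scores at that visit and all subsequent visits will be set to missing"

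Each of these three also has a rule for a missing language record: if the language is the same at all the other visits, it is taken as unchanged. E-RS has no such rule.

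The endpoint concerned is in the testing hierarchy of SAP Section 5.6: "Level 9: Secondary endpoint, UMEC 62.5 mcg: Mean change from baseline in E-RS score over Weeks 21-24 (inclusive) of the treatment period". Level 10 is the same test for UMEC 31.25 mcg. The repeated-measures model in SAP Section 7.3.5.1 uses six periods: "E-RS: Weeks 1-4, Weeks 5-8, Weeks 9-12, Weeks 13-16, Weeks 17-20, Weeks 21-24". SAP Section 5.3.2 places Weeks 21-24 at E-RS days 141 to 168 and sets a 4-week period value to missing when fewer than 14 days are available.

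**The concern.** A change of questionnaire language is a fair reason to doubt that later scores are comparable with baseline. It gives no reason to doubt scores recorded earlier in the same language as baseline. The E-RS rule removes those too.

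Treatment lasts 24 to 52 weeks and the diary is kept throughout (protocol Section 7.3.5), so for some participants the diary runs well past the tested window. A later event could then erase an endpoint already fully observed. This sits badly with SAP Section 5.3.2, which builds period values from all available data, and with the opening of SAP Section 7, which includes data collected on and after treatment.

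Two analyses are touched, and they should be kept apart. The mean-change analysis at Levels 9 and 10 is multiplicity-controlled. The E-RS responder analysis is an other endpoint, with no place in the hierarchy (comparison table in SAP Section 7).

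**Working it through.** The plan states no figure for the effect of this rule, so there is none to reproduce. The check is a day count.

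**Inputs**
- Six periods of 28 E-RS days, starting on days 1, 29, 57, 85, 113 and 141 (SAP Section 5.3.2).
- At least 14 days are needed for a period value (SAP Section 5.3.2).
- Assumptions: a complete diary, and a switch away from the baseline language first occurring on day d and not reversed.

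**Formulas**
- Literal rule: all post-randomization scores are deleted, of which d − 1 days were in the baseline language. Periods kept = 0 for every d.
- Forward-only rule, as for the other questionnaires: a period starting on day a keeps min(28, max(0, d − a)) days and survives if this is at least 14. For Weeks 21-24, a = 141.

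| First day in another language (d) | Baseline-language days deleted by the literal rule (d − 1) | Periods kept, literal | Periods kept, forward-only | Weeks 21-24 days kept, forward-only |
|---|---|---|---|---|
| 1 | 0 | 0 | 0 | 0 |
| 29 | 28 | 0 | 1 | 0 |
| 85 | 84 | 0 | 3 | 0 |
| 141 | 140 | 0 | 5 | 0 |
| 154 | 153 | 0 | 5 | 13 (too few) |
| 155 | 154 | 0 | 6 | 14 |
| 169 | 168 | 0 | 6 | 28 |
| 200 | 199 | 0 | 6 | 28 |

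The threshold for keeping Weeks 21-24 is d − 141 ≥ 14, so d ≥ 155. From d = 169 the whole 28-day window is in the baseline language, yet the literal rule still deletes it. The first row matters as well: if the whole post-randomization diary is in another language, the two rules give the same result.

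**Responder analysis.** SAP Section 7.4.4 treats missing data at the timepoint of interest as non-response, whatever the treatment status. The language rule leaves baseline in place, so the exemption for a missing baseline in SAP Section 11.7.2 does not apply. A participant with an observed improvement of at least 2 points over Weeks 21-24 would be counted as a non-responder.

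**Size.** The documents do not give the share p of participants who would lose otherwise usable E-RS data in this way. If they simply drop out of the mean-change model, the standard error grows by about 1/√(1 − p), a relative increase of roughly p/2 for small p.

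**The case against.** The strongest reply is that the rule treats the post-randomization diary as having one language. The E-RS is kept on a single combined spirometer and eDiary device, issued at Visit 1 and collected at the end of study or at early withdrawal (protocol Sections 7.1 and 7.3.5). ACQ, SGRQ and AQLQ are given visit by visit, so visit-based wording suits them. If the device language is fixed, every post-randomization score is in the wrong language and deleting all of them is right.

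Part of this stands. The sentence does not expressly address a switch during treatment, so a reader should not infer that the SAP knowingly chose to delete valid earlier scores. But no text says the device language is fixed, and nothing elsewhere narrows the rule. The fix also costs nothing in results under that reading, because the two rules then coincide.

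Three stronger readings are tempting and not supported:

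- **That recoded responders distort a confirmatory test.** Levels 9 and 10 test mean change only.
- **That the missing-data section alone settles the responder consequence.** Its sentence "Participants with missing data at scheduled clinic visit, regardless of treatment status, will be considered as non-responders" concerns clinic visits, and its E-RS bullet covers study withdrawal. The support comes from Section 7.4.4.
- **That anyone can lose a complete window to a later switch.** This needs a switch after day 168, so it applies only to participants followed beyond Week 24. By SAP Section 11.3.2, those with a planned final visit at Week 24 would not normally qualify. They can still lose earlier periods, or a usable Weeks 21-24 value if the switch falls on days 155 to 168.

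**Conclusion.** The point holds as a minor correction to a rule that, read literally, over-deletes. Any mid-treatment switch removes all six model periods, where a forward-only rule would keep between none and six depending on the day. A complete Weeks 21-24 window is lost only when the switch comes after day 168.

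The effect on the trial is probably a small loss of precision. It rests on an unstated and likely low frequency of language changes. Nothing in the documents suggests that switching differs by arm in this double-blind study, so no bias in the treatment comparison is shown. Levels 9 and 10 are the last steps of the hierarchy and are reached only if Levels 1 to 8 succeed. The stated power figures are not affected.

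**What to change.** Reword the E-RS sentence in SAP Section 11.6.3 so that scores are set to missing only from the first diary day in a language different from the baseline-period language onward. Then apply the existing 14-day minimum to each 4-week period, and add the missing-language rule already used for ACQ, SGRQ and AQLQ.

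The cost is small but not nil. The rule needs the diary language by date, which the documents do not show to be recorded, and slightly more programming. Availability of that record should be confirmed first. The change can be settled on blinded data before Source Data Lock, the SAP's own deadline for analysis decisions.
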